	PUCAI clinical response	Proportion for each weight/treatment	mITT	Weeks 12 and 52
		dose group along with the 95%	mITT who achieve PUCAI	Week 52
		2-sided CI with NRI and as observed.	clinical response at Week 12	
	PUCAI CFB	Descriptive statistics and 95% CI for	mITT	Weeks 12, 24, 36, and 52
		mean with mBOCF and as observed.		

		Analysis Method	Population	
Measure	Variable	(Section 6.1.3)	(Section 6.1.1)	Time Point(s)
Height	Height Velocity	Descriptive statistics and 95% CI for	mITT, by gender and age	Weeks 12, 24, and 52
	II : 14 CED	mean.	group	W 1 12 24 152
	Height CFB	Descriptive statistics and 95% CI for mean.	mITT	Weeks 12, 24, and 52
	Height Percentiles CFB	Descriptive statistics and 95% CI for mean.	mITT	Weeks 12, 24, and 52
Weight	Weight CFB	Descriptive statistics and 95% CI for mean.	mITT	At each scheduled visit.
	Weight Percentiles CFB	Descriptive statistics and 95% CI for mean.	mITT	Weeks 12, 24, and 52
Occipital head circumference	Head circumference	Descriptive statistics and 95% CI for mean.	mITT only on those patients less than 3 years at baseline	At all applicable visits (Week 12 + Q12W)
Puberty Development	Testosterone CFB	Descriptive statistics and 95% CI for mean.	mITT – males who are 9 years or older	Weeks 12, 36, and 52
	Estradiol CFB	Descriptive statistics and 95% CI for mean.	mITT – females who are 9 years or older without the date of onset of menstruation.	Weeks 12, 36, and 52
Abdominal Pain NRS	Abdominal Pain NRS score CFB	Descriptive statistics and 95% CI for mean with mBOCF and as observed.	mITT, summarized by age group	Weeks 12 and 52
. The	CCI			Week 12 and 52
CCI			mITT	Weeks 12 and 52
Histopathology	Histologic Remission	Proportion for each weight/treatment dose group along with the 95% 2-sided CI with NRI and as observed.	mITT	Weeks 12 and 52
	Histologic Improvement	Proportion for each weight/treatment dose group along with the 95% 2-sided CI with NRI and as observed.	mITT	Weeks 12 and 52

		Analysis Method	Population	
Measure	Variable	(Section 6.1.3)	(Section 6.1.1)	Time Point(s)
	Histologic-Endoscopic	Proportion for each weight/treatment	mITT	Weeks 12 and 52
	Mucosal Improvement	dose group along with the 95%		
		2-sided CI with NRI and as observed.		
	Histologic-Endoscopic	Proportion for each weight/treatment	mITT	Weeks 12 and 52
	Mucosal Remission	dose group along with the 95%		
		2-sided CI with NRI and as observed.		

Abbreviations: CFB change from baseline; CI = confidence interval; mBOCF = modified baseline observation carried forward; mITT = modified intent-to-treat; MMS = Modified Mayo Score; NRI = non-responder imputation; NRS = Numerical Rating Scale; PUCAI = Pediatric Ulcerative Colitis Activity Index; Q12W = every 12 weeks.

 Table AMBU.6.6.
 Description of Exploratory Efficacy/Health Outcomes Analyses

Measure	Variable	Analysis Method (Section 6.1.3)	Population (Section 6.1.1)	Time Point(s)
Mayo Score and components	Change from baseline in SF, RB, and Total Symptomatic Score	Descriptive statistics and 95% CI for mean with mBOCF and as observed.	mITT	At each scheduled visit
	Change from baseline in ES	Descriptive statistics and 95% CI for mean with mBOCF and as observed.	mITT	Weeks 12 and 52
	Time to first symptomatic response	Descriptive statistics and 95% CI for mean.	mITT	During Induction Period
	Time to first symptomatic remission	Descriptive statistics and 95% CI for mean.	mITT	During Induction Period
	MMS Alternative Clinical Remission	Proportion for each weight/treatment dose group along with the 95% 2-sided CI with NRI and as observed.	mITT	Weeks 12 and 52
CRP	CRP CFB	Descriptive statistics and 95% CI for mean with mBOCF and as observed.	mITT	Week 12 Week 52
Fecal calprotectin	Fecal calprotectin CFB	Descriptive statistics and 95% CI for mean with mBOCF and as observed.	mITT	Week 12 Week 52
PGIC	Mean PGIC Score	Descriptive statistics and 95% CI for mean as observed.	mITT	Week 4, Week 8, Week 12, and Week 52
PGRS	PGRS Score CFB	Descriptive statistics and 95% CI for mean with mBOCF and as observed.	mITT	At each scheduled visit.
Nocturnal Stool	Nocturnal Stool Score CFB	Descriptive statistics and 95% CI for mean with mBOCF and as observed.	mITT - In patients with a nocturnal stool score ≥1 at baseline	At each scheduled visit.
CCI				At each scheduled visit.
Bristol Stool Scale	Loose stool	Proportion for each weight/treatment dose group along with the 95% 2-sided CI with NRI and as observed	mITT, in patients with loose stool at baseline	At each scheduled visit.

		Analysis Method	Population	
Measure	Variable	(Section 6.1.3)	(Section 6.1.1)	Time Point(s)
EIMs	Resolution of Baseline EIMs	Proportion for each weight/treatment dose group along with the 95% 2-sided CI with NRI and as	mITT – in patients with EIMs at baseline	Weeks 12 and 52
		observed.		

Abbreviations: CFB = change from baseline; CI = confidence interval; CRP = c-reactive protein; ES = Endoscopic subscore; mBOCF = modified baseline observation carried forward; mITT = modified intent-to-treat; MMS = Modified Mayo Score; NRI = non-responder imputation; NRS = Numerical Rating Scale; PGIC = Patient's Global Impression of Change; PGRS = Patient's Global Rating of Severity; RB = rectal bleeding; SF = stool frequency.

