9.1.5. Determination of Responder Status/Loss of Response

At Week 12, patients who achieve an MMS clinical response as defined in [Table AMBU.5](#) may move into the maintenance period.

Week 12 Nonresponders are defined as those that **do not meet** the following criteria:

- A decrease in the MMS of [CCI] from baseline, and
- A decrease of [CCI] in the RB subscore from baseline or a RB score [CCI].

Nonresponding patients may receive extended induction dosing via IV infusion Q4W for 12 weeks as noted in [Table AMBU.4](#).

[CCI]

CCI

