4.2. Secondary Objectives

Table AMBU.4.2 shows the protocol-defined secondary objectives and endpoints of the study. In addition, the analysis of other exploratory endpoints are described in Section 4.3 and Section 6.10.

The estimand (ICH 2019) associated with each endpoint/analysis is documented in the following places:

- The population of interest is described in the protocol inclusion/exclusion criteria and in this document in Section 6.1.1 and Table AMBU.6.4.
- The endpoint/variables may be found in Table AMBU.4.2 and Table AMBU.6.4.
- The handling of intercurrent events and missing data may be found in Section 6.3 and Table AMBU.6.4.
- Population summary measures are described in Section 6.1.3, Table AMBU.6.5, and Table AMBU.6.6.

 Table AMBU.4.2.
 Secondary Objectives and Endpoints

Objectives	Endpoints
Secondary	
To evaluate the effect of treatment	The proportion of patients in modified Mayo score (MMS) clinical
with mirikizumab on achieving	remission at Week 12
clinical remission at Week 12	The proportion of patients in MMS clinical remission at Week 52
and/or Week 52	The proportion of patients in MMS clinical remission at Week 52
	among the MMS clinical remitters at Week 12 (durable clinical
	remission)
	The proportion of patients in MMS clinical remission at Week 52
	among the MMS clinical responders from Week 12
	MMS clinical remission is defined as:
	Stool frequency (SF) subscore = 0 , or SF = 1 , and
	Rectal bleeding (RB) subscore = 0, and
	Endoscopic subscore (ES) = 0 or 1 (excluding friability)
	MMS clinical response is defined below

Objectives	Endpoints
Secondary	
To evaluate the effect of treatment with mirikizumab on achieving clinical response at Week 12 and/or Week 52	The proportion of patients in clinical response at Week 12 The proportion of patients in clinical response at Week 52 The proportion of patients in clinical response at Week 12 who achieve clinical response at Week 52 Clinical response is based on the MMS and is defined as: A decrease in the MMS of ≥2 points and ≥30% decrease from baseline, and A decrease of ≥1 point in the RB subscore from baseline or a RB score of 0 or 1

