6.3. Handling of Dropouts or Missing Data

Intercurrent events (FDA 2021) are events which occur after the treatment initiation and make it impossible to measure a variable or influence how it should be interpreted. Examples of such

events include treatment discontinuation due to death or adverse events (AEs), rescue treatment, and loss to follow-up. The missing data methods described below handle intercurrent events in different ways and thus are relevant to different estimands.

The Schedule of Activities outlined in the protocol specifies the allowable windows for assessments. Assessments performed outside these windows will not be excluded from any analysis, but will be reported as a protocol deviation (see Section 6.15). While every effort will be made to reduce missing data, the missing data imputation method of NRI will be used when patients are permanently discontinued from study drug or otherwise have missing data. For the "as observed" analysis, only data from completers at the visit are relevant, and therefore the analysis does not need to deal with missing data.

For any interim analyses that occur, patients who, based on their treatment start date, would not have completed the visit corresponding to the selected endpoint at the time of the database lock will not be included in the analysis of that endpoint unless otherwise specified. Patients who have discontinued or otherwise have missing data and would have otherwise completed that visit at the time of database lock will be counted as non-responders for the interim analysis. For example, if a patient who discontinued at Week 12 of the study would have been in Week 24 of the study at the time of database lock, would not be included in the analysis of endpoints at Week 36 or Week 52. If that same patient who discontinued would have been at Week 48 at the time of the interim database lock if they had remained in the study, they would be counted as a non responder for Week 36, but not included in the Week 52 analysis.

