6.3.1. Non-Responder Imputation (NRI)

For analysis of categorical efficacy and health outcomes variables, missing data will be imputed using an NRI method. Patients will be considered non-responders for the NRI analysis if they do not meet the categorical efficacy criteria or have missing clinical efficacy data at a time point of interest.

The NRI method may be used when the estimand of interest uses the composite strategy (FDA 2021) for handling intercurrent events. In this strategy, patients with any intercurrent events that lead to the permanent discontinuation of assigned study treatment are defined to have failed treatment for all subsequent time points.

In addition, patients who were not adequately assessed to determine if they meet the clinical requirements for response at the time point of interest are also considered to have failed treatment.

For any interim analyses that occur, patients who, based on their treatment start date, would not have completed the visit corresponding to the selected endpoint at the time of the database lock will not be included in the analysis of that endpoint. Patients who have discontinued or otherwise have missing data and would have otherwise completed that visit at the time of database lock will be counted as non-responders for the interim analysis.

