	Each subscore is on a 4-point scale, ranging from 0 to 3.	PGA subscore	Possible values are: (0) Normal (1) Mild disease	Single item. Missing if missing.

Measure	Description	Variable	Derivation / Comment	Definition of Missing
			(2) Moderate disease	
			(3) Severe disease	
		Modified Mayo Score	Calculated as: SF + RB + ES.	Missing if SF, RB or ES
		(MMS)		subscores are missing.
		Partial Mayo Score	Calculated as: SF + RB + PGA.	Missing if SF, RB or PGA subscores are missing.
		Alternate MMS Clinical Remission	SF subscore = 0, or SF = 1 with a ≥1-point decrease from baseline, and RB subscore = 0, and ES subscore = 0 or 1 (excluding friability)	Missing if SF, RB, or ES subscores are missing.
		MMS Clinical	SF subscore = 0 or 1	Missing if SF, RB, or ES
		Remission	RB subscore $= 0$, and	subscores are missing.
			ES subscore = 0 or 1 (excluding friability)	J
		MMS Clinical Response	A decrease in the MMS of ≥2 points and ≥30% decrease from baseline, and A decrease of ≥1 point in the RB subscore from baseline or a RB score of 0 or 1	Missing if baseline or Week 12 MMS is missing.
		Endoscopic Remission	ES = 0 or 1 (excluding friability).	Missing if ES is missing.
		Symptomatic Remission	$SF = 0$, or $SF = 1$ with a ≥ 1 -point decrease from baseline and $RB = 0$	Missing if SF or RB is missing.
		Time to first symptomatic remission	For patients who are observed to meet the remission criteria during the Induction Period, time will be from the start of the Induction Period to the first measurement date where the patient met the remission criteria based on weekly averages.	Patients not observed to meet remission criteria during the Induction Period will be censored after the date of their last measurement during the Induction Period.

Measure	Description	Variable	Derivation / Comment	Definition of Missing
			CCI	
		Time to first symptomatic response	For patients who are observed to meet the response criteria during the Induction Period, time will be from the start of the Induction Period to the first measurement date where the patient met the response criteria based on weekly averages.	Patients not observed to meet response criteria during the Induction Period will be censored after the date of their last measurement during the Induction Period.
		Endoscopic subscore of 0	ES = 0.	Missing if ES is missing.
		Total Symptomatic Score	Calculated as SF + RB.	Missing if SF or RB is missing.

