Appendix 1. Diary Calculations

Weekly summary measures of diary data will be created for each patient. The 7-day period associated with each week will be defined using a visit centric approach. The table below displays the interval for each week.

Week (Visit)	Start Day ^a	End Daya	
Screening	Max(Informed Consent Date, Week 0 Visit Date - 14)	Week 0 Visit Date – 8	
Baseline	Week 0 Visit Date – 7	Week 0 Visit Date – 1	
Week 2 (V3)	Max(Week 0 Visit Date, Week 2 Visit Date – 7)	Week 2 Visit Date – 1	
Week 4 (V4)	Max(Week 2 Visit Date, Week 4 Visit Date – 7)	Week 4 Visit Date – 1	
Week 8 (V5)	Max(Week 4 Visit Date, Week 8 Visit Date – 7)	Week 8 Visit Date – 1	
Week 12 (V6)	Max(Week 8 Visit Date, Week 12 Visit Date – 7)	Week 12 Visit Date – 1	
Continue the algorithm as above.			
Week 48 (V15)	Max(Week 44 Visit Date, Week 48 Visit Date – 7)	Week 48 Visit Date – 1	
Week 52 (V16)	Max(Week 48 Visit Date, Week 52 Visit Date – 7)	Week 52 Visit Date – 1	

a If End Day < Start Day, do not assign specified visit week. Visit date will be calculated by selecting the first date from the following list (ie, first in list order): (1) date of endoscopy preparation if endoscopy preparation was performed, (2) date of endoscopy if endoscopy was performed, (3) date of treatment if treatment was given,
 (4) office visit date if available, or (5) imputed date of visit center of the protocol-defined window for that visit.

For the Mayo SF and RB subscores, the most recent 3 nonmissing days of the 7-day period in the table above will be averaged and rounded to the nearest integer to calculate the weekly score for each patient. Patients with less than 3 measurements in the 7-day period will be considered missing.

All diary data collected on the following days will be excluded from any calculations:

- any day(s) of bowel preparation
- day after any day(s) of bowel preparation (will most often be associated with date of endoscopy)
- day of endoscopy
- day after endoscopy, and
- two days after endoscopy (patients will be answering questions in a 24-hour recall fashion, so two days following endoscopy, they may be reporting their patient-reported outcomes from the day after the endoscopy).

For the Bristol Stool Scale the worst (ie, maximum) of the available measures during the 7-period in the table above will be used to calculate a weekly score for each patient. If fewer than

4 days are available (ie, not missing), the patient will be considered to be missing data for that week.

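### The SAP's missing-data rule for MMS clinical response names only Week 12, so a Week 52 responder without a Week 12 score would be counted as a non-responder

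*SAP*

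**What the plan says.** SAP Table AMBU.6.4, within Section 6.10.1, gives each efficacy variable a derivation and a definition of missing. For MMS clinical response the definition is "Missing if baseline or Week 12 MMS is missing". Another row of the table makes the MMS itself missing when the stool frequency, rectal bleeding or endoscopic subscore is missing.

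Clinical response is not only a Week 12 endpoint. SAP Table AMBU.4.2 lists "The proportion of patients in clinical response at Week 52" and, separately, "The proportion of patients in clinical response at Week 12 who achieve clinical response at Week 52". Table AMBU.6.5 analyses the variable at Weeks 12 and 52 in the mITT population, and at Week 52 among Week 12 responders, each time with NRI and as observed.

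The general rules work visit by visit:

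- Section 6.3.1 makes patients NRI non-responders if they do not meet the criteria "or have missing clinical efficacy data at a time point of interest".
- Section 6.3 says of the as-observed analysis that "only data from completers at the visit are relevant".
- Section 6.1.2 treats a change from baseline as missing when either the baseline value or the value at that visit is absent.

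On where the rules are to be found, Section 4.2 says: "The handling of intercurrent events and missing data may be found in Section 6.3 and Table AMBU.6.4". It does not say which prevails if they differ.

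**The concern.** The neighbouring rows for variables analysed at both Week 12 and Week 52 (MMS clinical remission, endoscopic remission, endoscopic subscore of 0) name no week in their definition of missing. The clinical response row does, and it names the wrong one for half of its use. At Week 52 it makes a patient's status depend on a score taken 40 weeks earlier that plays no part in the Week 52 criteria, which compare Week 52 with baseline.

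At stake is the unconditional Week 52 response proportion. A patient who meets the Week 52 criteria could be reported as a failure, and the as-observed analysis could leave out a patient who was observed. The groups are small enough for one patient to be visible in the result.

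**Working it through.** The plan states no figure that depends on this rule, so there is nothing of its own to reproduce. The check has three steps.

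**1. Can the pattern occur?** It needs a patient with no Week 12 MMS who stays in the study to Week 52.

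- SAP Appendix 1, on the stool frequency and rectal bleeding subscores: "Patients with less than 3 measurements in the 7-day period will be considered missing". Either subscore missing makes the MMS missing. So does an unreadable Week 12 endoscopy, a possibility that Protocol Section 6.4.1 recognises for screening.
- Failing to show a Week 12 response does not end participation. Protocol Section 9.1.5: "Nonresponding patients may receive extended induction dosing via IV infusion Q4W for 12 weeks as noted in" Table AMBU.4. Protocol Section 5.1 then allows maintenance dosing to Week 48 if the investigator judges that the patient has improved.

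The pattern is possible. The documents do not say how often to expect it.

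**2. What does each rule give at Week 52?** Baseline MMS is present throughout. The literal reading applies the table cell together with Sections 6.3 and 6.3.1. The per-visit reading replaces Week 12 in the cell by the visit analysed.

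| Week 12 MMS | Week 52 MMS | Week 52 criteria | NRI: literal / per visit | As observed: literal / per visit |
|---|---|---|---|---|
| present | present | met | responder / responder | responder / responder |
| present | present | not met | non-responder / non-responder | non-responder / non-responder |
| present | missing | – | non-responder / non-responder | excluded / excluded |
| missing | present | met | **non-responder / responder** | **excluded / responder** |
| missing | present | not met | non-responder / non-responder | **excluded / non-responder** |
| missing | missing | – | non-responder / non-responder | excluded / excluded |

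The two readings differ in two rows, both with Week 12 missing and Week 52 present. Under NRI they differ only when the criteria are met, so the NRI error always lowers the rate.

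**3. How large is it?** Inputs: about 30 patients, of whom about 10 weigh more than 40 kg and about 20 weigh 40 kg or less (SAP Section 5.2); 95% Wilson intervals (SAP Section 6.1.3). Assumptions, not in the documents: a true Week 52 response rate of 50%; 0 to 3 affected patients, all meeting the criteria; everyone else observed at Week 52.

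Each affected responder lowers the NRI rate by 1/N: 1/30 = 3.3 points, 1/20 = 5 points, 1/10 = 10 points. The Wilson limits are [p + z²/2n ± z√(p(1−p)/n + z²/4n²)] / (1 + z²/n), with z = 1.96.

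| Affected | N = 30, NRI | N = 30, as observed | N = 10, NRI | N = 10, as observed |
|---|---|---|---|---|
| 0 (same as per-visit rule) | 15/30 = 50.0% (33.2 to 66.8) | 15/30 = 50.0% | 5/10 = 50.0% (23.7 to 76.3) | 5/10 = 50.0% |
| 1 | 14/30 = 46.7% (30.2 to 63.9) | 14/29 = 48.3% | 4/10 = 40.0% (16.8 to 68.7) | 4/9 = 44.4% |
| 2 | 13/30 = 43.3% (27.4 to 60.8) | 13/28 = 46.4% | 3/10 = 30.0% (10.8 to 60.3) | 3/8 = 37.5% |
| 3 | 12/30 = 40.0% (24.6 to 57.7) | 12/27 = 44.4% | 2/10 = 20.0% (5.7 to 51.0) | 2/7 = 28.6% |

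If the affected patient does not meet the criteria, NRI is unchanged but the as-observed rate rises, for example from 5/10 = 50.0% to 5/9 = 55.6%. The as-observed error can therefore go either way.

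**The case against.** The strongest reply is that the general rules already settle the matter. Sections 6.1.2, 6.3 and 6.3.1 all work by visit, the neighbouring rows name no week, and a sensible programmer would read the cell as a leftover from drafting. The Week 12 MMS also decides whether a patient goes to maintenance or extended induction, so sites have every reason to obtain it and few patients should lack it. The size quoted is simply 1/N, the effect of reclassifying any one patient.

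Most of this stands, and it is why the point is minor. It does not remove the conflict. Section 6.3.1 says what to do with missing data; Table AMBU.6.4 says what counts as missing, and no order of precedence is given. The interim analysis includes MMS response at Week 52, and Section 6.16.2 refers to Section 6.10.1, which holds this table, for the details. A programmer who follows the cell is following the SAP.

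A reader might go further and infer the mirror-image error: that a patient with a Week 12 MMS but no Week 52 MMS counts as not missing, and so is kept in the Week 52 as-observed analysis. The documents do not support that. Section 6.3.1 makes such a patient an NRI non-responder, Section 6.3 limits the as-observed analysis to completers at the visit, and response cannot be computed without a Week 52 score. The third row of the first table shows no difference.

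**Conclusion.** The cell is wrong as written, with minor consequences. The error is confined to the unconditional Week 52 response proportion, and within it to patients with baseline and Week 52 MMS but no Week 12 MMS. Under NRI each such patient who meets the criteria costs 3.3 points at N = 30 or 10 points in a group of 10, always downward. In the as-observed analysis each such patient is dropped, with an effect in either direction.

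It would be too strong to say that Week 52 response is misclassified in general. The endpoint among Week 12 responders is unaffected, because a Week 12 responder has a Week 12 MMS by definition. The endpoint is secondary and descriptive, with no treatment comparison planned, and the primary PK endpoint and the sample size do not depend on it. The number of affected patients is unknown and may be zero; the 0 to 3 range and the 50% rate above are illustrations only.

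**What to change.** In SAP Table AMBU.6.4, change the definition of missing for MMS clinical response to: *Missing if the baseline MMS or the MMS at the visit being analysed is missing.* This agrees with Sections 6.1.2, 6.3 and 6.3.1 and leaves the Week 12 analysis unchanged. The cost is one table cell, plus a check that the derivation program uses the analysis visit. It needs no new data and no change to the design.

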9.1.1. Mayo Score

This study utilizes components and permutations of the Mayo score (Schroeder et al. 1987) to assess UC disease activity for the primary and secondary endpoints (see [Appendix 7](#)). **Complete and accurate recording of the Mayo SF and RB subscores by patients or their parent/caregiver in their daily electronic diary is necessary for the success of the study.** Adequate bowel preparation and an endoscopy with adequate visualization of the mucosa will enable calculation of the Mayo ES.

Note: The investigator is responsible for ensuring that study participants receive adequate training on and appropriate understanding of:

- the importance of complete bowel preparation prior to endoscopies/flexible sigmoidoscopies
- how to record “remission/ normal” SF at the beginning of the study
- how to evaluate their UC symptoms and to record them on the CCI diary, and
- the importance of being compliant with the CCI diary recording.

The Mayo score is a composite instrument comprised of the following 4 subscores:

Stool Frequency (SF): The SF subscore is a patient-reported measure. This item reports the number of stools in a CCI, relative to the normal number of stools for that patient in the same period, on a 4-point scale (see Appendix 7). CCI

The total number of stools passed CCI will be recorded by the patient or caregiver in a daily electronic diary. The reference “normal” SF for that patient will be recorded electronically at the screening visit. Normal SF for that patient is based on reported SF when the patient was in remission or reported SF before initial onset of signs and symptoms of UC. Study software will use the patient-reported daily SF and the reference normal SF to automatically calculate the Mayo SF subscore. Further details on the analysis of CCI diary items are contained in the SAP.

Rectal Bleeding (RB): The RB subscore is a patient-reported measure. This item reports the most severe amount of blood passed with stool for a given day, on a 4-point scale (see Appendix 7). The patient or caregiver will record this in a CCI electronic diary.

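### Time to first symptomatic remission and response (exploratory): within induction, onset can be detected only in the 7 days before Weeks 2, 4, 8 and 12, and consecutive weekly windows would date it better at little cost

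*SAP*

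**What the plan says.** SAP Section 6.10.1, Table AMBU.6.4, measures time to first symptomatic remission from the start of induction to "the first measurement date where the patient met the remission criteria based on weekly averages". The response row is worded in parallel. Children not seen to meet the criteria during induction are censored after their last measurement in that period. What counts as a measurement date is not defined in the visible text.

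Symptomatic remission and response are built from the stool-frequency (SF) and rectal-bleeding (RB) subscores. Table AMBU.6.4 refers the derivation of both subscores to Appendix 1, the only place where a weekly diary value is defined. It states: "The 7-day period associated with each week will be defined using a visit centric approach". After baseline, its induction rows are Week 2 (V3), Week 4 (V4), Week 8 (V5) and Week 12 (V6). The instruction to carry the algorithm on comes after the Week 12 row and leads to Week 48, so it adds no weeks inside induction. Within each period, for SF and RB, "the most recent 3 nonmissing days of the 7-day period in the table above will be averaged and rounded to the nearest integer".

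The source data are finer than this. Protocol Section 9.1.1 says that the number of stools "will be recorded by the patient or caregiver in a daily electronic diary", and it describes RB as part of the same daily diary record.

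**The concern.** These two endpoints exist to say when symptoms first improve. If the only scores available are those before four visits, the result can take about four values, set by the visit calendar. Weeks 1, 3, 5 to 7 and 9 to 11 have no score. A child who enters remission in Week 5 cannot be seen to do so until the Week 8 window. A child in remission only during Weeks 5 to 7 is not seen at all, and is censored if no later window qualifies.

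SAP Table AMBU.6.6 summarises these times with descriptive statistics and a confidence interval for the mean, so late dating carries straight into the reported figure. The diary entries needed for weekly dating are already collected.

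**Working it through.** The documents give no figure for diary coverage or dating delay, so there is none to reproduce. The check counts days from the Appendix 1 formula.

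**Inputs.** Induction is 12 weeks (Protocol Section 5.4), or 84 diary days, numbered 0 to 83 from the Week 0 visit. Visits are placed at nominal days 0, 14, 28, 56 and 84; this is an assumption, because real visits vary. For Week 8, for example, Appendix 1 gives the start day as "Max(Week 4 Visit Date, Week 8 Visit Date – 7" (closing bracket omitted) and the end as the day before the visit.

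**Step 1: windows.** Start = max(previous visit day, visit day − 7); end = visit day − 1.

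| Visit | Start | End |
|---|---|---|
| Week 2 | max(0, 7) = 7 | 13 |
| Week 4 | max(14, 21) = 21 | 27 |
| Week 8 | max(28, 49) = 49 | 55 |
| Week 12 | max(56, 77) = 77 | 83 |

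The windows hold 4 × 7 = 28 of 84 days. The gaps are days 0-6, 14-20, 28-48 and 56-76, that is 7 + 7 + 21 + 21 = 56 days (67%). If each visit may shift by up to 7 days (assumed, because the visit windows are redacted), the share outside any window runs from 64% to 77%.

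**Step 2: days that enter SF and RB.** Only three days per window are averaged. Now: 4 × 3 = 12 of 84 (14%). With twelve consecutive weeks under the same rule: 12 × 3 = 36 of 84 (43%), leaving 48 still unused.

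**Step 3: dating delay.** For sustained onset in week w, delay = next scored week (2, 4, 8 or 12) − w, relative to consecutive weekly windows.

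| w | 1 | 2 | 3 | 4 | 5 | 6 | 7 | 8 | 9 | 10 | 11 | 12 |
|---|---|---|---|---|---|---|---|---|---|---|---|---|
| Weeks late | 1 | 0 | 1 | 0 | 3 | 2 | 1 | 0 | 3 | 2 | 1 | 0 |

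The sum is 14. With onset uniform over the 12 weeks (assumption), the mean is 14/12 = 1.17 weeks and the maximum is 3. A day-by-day version gives a mean of 8.4 to 8.5 days and a maximum of 21 days, which agrees. The mean depends on when onset occurs: (1+0+1+0)/4 = 0.5 week for onset in Weeks 1-4, and (3+2+1+0+3+2+1+0)/8 = 1.5 weeks for Weeks 5-12.

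**Step 4: missed episodes.** Weeks 5-7 are days 28-48 and Weeks 9-11 are days 56-76, exactly the two long gaps. For illustration, assume one symptom-free episode, starting uniformly among the days that let it fit within the 84, and detected when at least two of a window's last three days are symptom-free.

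| Episode length | Missed, visit windows | Missed, consecutive weeks |
|---|---|---|
| 7 days | 71% | 0% |
| 14 days | 39% | 0% |
| 21 days | 22% | 0% |
| 28 days | 0% | 0% |

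**The case against.** **Appendix 1 may not govern these rows.** The two time-to-event rows carry no visible pointer to it, weekly averages could mean every week, and a blacked-out cell sits between the rows. But the endpoints consist of SF and RB subscores, which the same table does refer to Appendix 1, and no other weekly value is defined in the visible text. If consecutive weeks were meant, the SAP needs to say so, which leads to the same edit.

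**Visit windows may be deliberate.** Protocol Table AMBU.2 lists SF and RB at Weeks 2, 4, 8 and 12 within induction. The SAP revision history records a change to the weeks used in the diary calculations, and symptomatic remission is also analysed by visit (Table AMBU.6.5). Shared windows keep the results aligned; under the fix a child could have an event in Week 6 without being in remission at any visit. This stands, and it is why the point is an improvement rather than a correction.

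**More looks pull the other way.** Going from 4 to 12 looks, each on a rounded three-day average, makes it more likely that one brief good spell counts as first remission. This also stands, and its size has not been estimated.

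**Little hangs on it.** Both endpoints are exploratory, in an open-label PK study of about 30 patients with no treatment comparisons, and neither is named among the interim efficacy summaries (SAP Section 6.16.2). In addition, a plain mean of censored times remains awkward whichever windows are used. All of this stands and sets the priority low.

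**Conclusion.** As written, the two endpoints can detect onset in induction only through the four visit windows. Relative to consecutive weekly windows, sustained onset is dated 0 to 3 weeks late, with a mean of about 1.2 weeks under nominal visit dates and an assumed uniform onset. Episodes confined to Weeks 5-7 or 9-11 are missed, and such a child may be censored. This is a cheap improvement of low priority.

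Three stronger readings are not supported:
- A reader might infer that the SAP is wrong. Visit windows are coarse for an onset endpoint, but they match the protocol's visit schedule for SF and RB.
- A reader might take the 56 of 84 days outside the windows as the share of diary data lost, to be recovered by the fix. Under the three-day rule the relevant counts are 12 days used now and 36 after the change, so most days would still not enter a score.
- A reader might take 0 to 3 weeks as the lag from true onset. It is a comparison between two scoring schemes, and 8 of the 12 onset weeks are late by one week or less.

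The primary PK objective and the Week 12 and Week 52 proportions are unaffected.

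**What to change.** For these two endpoints only, add to Appendix 1 consecutive 7-day windows counted from first dose (Days 1-7, 8-14 and so on) up to the Week 12 visit. Apply the existing three-day rule and endoscopy exclusions. Define the measurement date as the last day of the first qualifying week, and refer to these windows from the two rows of Table AMBU.6.4. Keep the visit-centric windows for every by-visit endpoint.

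The cost is a short SAP addition and one derived dataset, with no new data and no burden on children or sites. The SAP should acknowledge the move from 4 looks to 12.

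If the sponsor prefers visit windows, the minimum is to say so in Table AMBU.6.4, define the measurement date, and describe both endpoints as visit-based, with onset known only to lie between scored windows.
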